## **How firmly should I apply CHG cloths to a wound?**

It depends on whether the wound is over a bony prominence or not. If the wound is not over a bony prominence, then CHG should be applied with a firm massage to ensure adequate contact and anti-bacterial activity. However, if the wound is in the location of a bony prominence, a *gentle massaging motion* should be used to avoid causing additional soft tissue damage or extension of the wound due to pressure against the bone.

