## IMPORTANT REMINDERS for CHG Cloth Bathing and Showering

- a.** Do not use regular soap with CHG. Many soaps inactivate chlorhexidine. CHG works better than soap and water in deeply cleansing the skin.
- b.** Ensure thorough cleaning, with special attention to commonly soiled areas such as the neck, skin folds, and perineal areas. CHG is safe to use on perineal areas, including external mucosa.
- c.** For candidal rashes, note that CHG is active against candida. However, be sure that the CHG is dry between body folds. Fan the area with the blue insulator to aid drying. If not completely dry, rashes may worsen.
- d.** CHG is safe for superficial wounds, including stage 1 and 2 decubitus ulcers, superficial burns, as well as rashes and abrasions. These areas are at high risk for infection and CHG kills germs and helps prevent infections. Do not use on large or deep wounds, (e.g. packed wounds)
- e.** Use CHG for all bathing purposes, including full-body bathing, cleaning after incontinence clean up, or any other reasons for additional cleaning. This includes the face; however avoid contact with eyes and ears.
- f.** If moisturizer is needed, provide resident with CHG-compatible lotion
- g.** Allergic reactions are rare, but can occur. If your resident experiences a reaction possibly related to the study product, contact the resident's treating physician for all clinical decisions on whether to stop the product or provide any medication to address a possible reaction. Complete a "Study Related Event" form located in your Toolkit binder and submit it to the nursing home's nursing director.
- h.** Maintain facility policies for covering devices, including dressings to prevent water penetration and introduction of water borne bacteria.

---

PROTECTING NURSING HOME RESIDENTS FROM INFECTIONS AND READMISSIONS

---

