### **Are there special instructions for large or obese residents?**

In order to be effective in removing germs, it is important that CHG cloths are applied with a firm massage on all skin areas (gently massaged onto wounds). This is particularly important in skin folds of large or obese residents since dirt, sweat, and germs can accumulate there. Make sure that after the CHG cloth is applied, the skin fold areas are allowed to fully dry. Lift skin folds to clean by firmly massaging the entire skin with the CHG cloth. Sometimes placing rolled towels to prop open skin folds may help with the application or drying process. Use as many CHG cloths as necessary.

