## **For what types of wounds is CHG safe?**

CHG can be gently applied to any superficial wound, including stage 1 and 2 decubitus ulcers, friable skin/rash, and superficial burns. We do not recommend using CHG on large or deep open wounds. Skin near and surrounding any wound should always be cleaned well.

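### For superficial wounds not over a bony prominence, the Group 2 toolkit gives two different pressures for applying chlorhexidine cloths and does not say which applies

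*Combined protocol and SAP*

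**What the plan says.** Three answers in the Group 2 Frequently Asked Questions touch on pressure at a wound.

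- **Chlorhexidine for Bathing FAQ, *Are there special instructions for large or obese residents?*** The answer opens with a general statement: "it is important that CHG cloths are applied with a firm massage on all skin areas (gently massaged onto wounds". It sets skin (firm) against wounds (gentle) and attaches no condition on where the wound lies.
- **Wound Care FAQ, *For what types of wounds is CHG safe?*** The answer reads: "CHG can be gently applied to any superficial wound, including stage 1 and 2 decubitus ulcers, friable skin/rash, and superficial burns". Again there is no site condition, although the verb is permissive.
- **Wound Care FAQ, *How firmly should I apply CHG cloths to a wound?*** Here pressure depends on site: "If the wound is not over a bony prominence, then CHG should be applied with a firm massage". The gentle motion applies "if the wound is in the location of a bony prominence", and the reason given is further soft tissue damage from pressure against the bone.

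The Nursing Protocol's Important Reminders, item d, deal with eligibility only: "CHG is safe for superficial wounds, including stage 1 and 2 decubitus ulcers, superficial burns, as well as rashes and abrasions". They give no pressure.

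**The concern.** The firmness answer divides wounds by site. The other two answers do not divide them at all. A staff member reading the bathing FAQ gets what looks like a complete rule, gentle on wounds. A colleague reading the firmness answer gets a different rule for every wound away from bone. The eligibility answer makes the difference concrete, because it names friable skin and superficial burns among the sites where gentle application is mentioned, and those can lie anywhere on the body.

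What is at stake is whether staff can carry out one step of the assigned intervention in one way. This is an operative instruction for applying the study product to broken skin. The toolkit already treats wound application as a weak step: it lists CHG use on superficial wounds among the most commonly missed bathing practices, and the Wound Care FAQ says some staff are uneasy about it.

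**Working it through.** No rate, sample size or error level enters this point, so there is nothing to compute. The check sets the answers side by side for the two cases that the firmness answer distinguishes, then looks for a tie-breaker elsewhere in the toolkit.

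**Step 1. Compare by case.**

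| Answer | Wound over a bony prominence | Superficial wound elsewhere |
|---|---|---|
| Bathing FAQ, large or obese residents | gentle | gentle |
| Wound Care FAQ, types of wounds (permissive) | gentle | gentle |
| Wound Care FAQ, how firmly | gentle | firm |
| Agreement | yes | no |

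The conflict is confined to the right-hand column.

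**Step 2. Is the bathing answer limited to obese residents?** Its opening sentence is general. The answer then says the technique matters particularly in the skin folds of large or obese residents, which presupposes that it applies to others as well. Even on a narrow reading, an obese resident with a wound away from bone would be covered by both rules.

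**Step 3. Look for a tie-breaker.**

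- *Nursing Protocol, cloth bathing and showering sections and Important Reminders:* these allow use on superficial wounds and give no wound pressure.
- *Staff Skills Assessment, CHG Cloth Observation Checklist:* one line scores firm massage of skin. Separate lines for superficial and surgical wounds record whether CHG was used, not how firmly.
- *List of commonly missed practices and staff bathing handout:* both call for firm massage onto skin and, separately, mention surface wounds. Neither gives a wound pressure.
- *Just in Time Training:* firm massage to skin, with no pressure rule for wounds.
- *Resident Talking Points on wounds and rashes:* these encourage use and are silent on pressure.

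None of these settles the question. Neither gentle answer refers to the firmness answer or carries its site condition, and no text gives an order of precedence.

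**The case against.** The strongest reply is that only one entry actually asks how firmly to treat a wound. It gives a two-branch rule with a reason for each branch. The bathing FAQ mentions wounds in a short parenthesis under another question, and the eligibility answer is permissive and concerns which wounds qualify. On this view the firmness answer refines two passing remarks.

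Part of this stands. The eligibility answer does not rule out firm massage, so it is supporting text only, and the conflict rests mainly on the bathing answer against the firmness answer. But the bathing answer is a direct, unconditional instruction in a different FAQ, with no pointer to the refinement. A reader who stops there would not know that a site rule exists.

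Three stronger readings are tempting, and the documents do not support them.

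- *That resident safety is shown to be at risk.* The toolkit links pressure to tissue damage only for wounds over bone, where all three answers agree on gentle. For the disputed wounds it states no hazard from firm massage; the only reason offered is adequate contact and antibacterial activity.
- *That delivery differed between homes.* All 14 intervention homes were given the same toolkit, supported by on-site training, a video and buddy pairing. Study staff could also be asked about wounds. Nothing in the documents shows varied practice.
- *That the checklist scores staff for massaging wounds firmly.* Its firm-massage line concerns skin. On wound pressure it is silent.

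**Conclusion.** The inconsistency is real and narrow. For superficial wounds not over a bony prominence, the toolkit gives both a gentle and a firm instruction and does not say which governs. For wounds over a bony prominence there is no conflict.

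Its size cannot be stated as a number, because the documents give no count of such wounds or of cloth applications to them. It would be wrong to treat every such application in the 14 homes over the 18-month intervention period as affected. What can be said is that the same wound can be handled in two ways, each faithful to a page of the toolkit. The consequence is limited to consistent handling by staff. Randomization, the outcome definitions, the mixed logistic model and the power estimates are untouched.

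The conclusion assumes that the on-site training and video did not supply a single wound rule. Their content is not in the documents. If they did supply one, the written toolkit still needs to match it.

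**What to change.** The investigators should reconcile the three FAQ answers (large or obese residents; types of wounds; how firmly) into one clinically approved instruction for pressure on wounds. Which pressure is right is a clinical decision for them, and none is proposed here. The agreed wording should then appear wherever wound application is described, for example in item d of the Nursing Protocol's Important Reminders. A matching wound-pressure line on the observation checklist is optional.

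The cost is a few lines of toolkit text and a reprint of the pages concerned. Neither the design nor the analysis changes.

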## **I am having trouble with applying bandages after bathing my residents with CHG. Does CHG weaken bandage adhesive?**

If you are having trouble applying a bandage after bathing a resident with CHG, it's usually because not enough time has elapsed to allow for complete drying. After bathing a resident, allow the CHG to completely dry for about 5 minutes. When completely dry, CHG will not affect the bandage adhesive. If you are in a rush, fanning the CHG dry is acceptable, but do not wipe off or blot dry. If the resident's skin still feels tacky, it may prevent the bandage from sticking properly.

PROTECTING NURSING HOME RESIDENTS FROM INFECTIONS AND READMISSIONS

## Frequently Asked Questions

### Nasal Iodophor

#### **What is iodophor?**

Iodophor is another name for “povidone-iodine,” which is an over-the-counter antiseptic that is most known for its use in cleaning scrapes, cuts, and wounds and preventing infections. It is also FDA cleared for use in the nose.

#### **What is the purpose of putting it in the nose?**

Iodophor removes germs that commonly live in the nose, including methicillin-resistant *Staphylococcus aureus*, or MRSA. Many studies have shown that nursing home residents are much more likely to harbor MRSA than people in the community or patients in hospitals. In fact, recent data across many nursing homes in Southern California and elsewhere have shown that over 40% of nursing home residents harbor MRSA. Because having MRSA in the nose is a known risk factor for later infection, our nursing home has decided to adopt the use of iodophor for our residents to prevent transmission and infection.

## **Is decolonization a proven strategy?**

Yes. Use of chlorhexidine baths and nasal decolonization has been proven in large clinical trials to reduce MRSA and other bacteria and prevent infection. This has been shown in hospital ICUs and in post-discharge nursing home settings.

## **How safe is iodophor?**

Povidone-iodine is an over-the-counter antiseptic product. It has been used in healthcare for over 60 years. Nasal iodophor has been used in thousands and thousands of patients prior to surgery, in ICUs, and in nursing homes as a way to prevent MRSA and methicillin-sensitive *Staphylococcus aureus* (MSSA) infection. Side effects from iodophor are uncommon, mild and resolve with discontinuation. They may include nasal irritation, runny nose, and sneezing. As with any product, rare serious allergic reactions can occur.

## **Why are we giving iodophor instead of mupirocin?**

Iodophor has many advantages over mupirocin. First, it is an antiseptic product, not an antibiotic. Second, there is evidence that it is better tolerated than mupirocin. Third, mupirocin resistance has been reported throughout the U.S. and is fairly common in many Southern California nursing homes.

## **What if the resident wants to blow their nose after application?**

Residents should be told to blow their nose before the application to help clear the nasal area. They should be encouraged not to blow their nose immediately after application for best effects.

## **Is it okay to provide decolonization if my resident is not alert?**

This routine decolonization regimen of chlorhexidine soap plus nasal iodophor has been approved as a standing nursing protocol which is covered in the resident's admission agreement as usual care. It is provided with an MD order. While residents are able to refuse, all residents who are unable to refuse will be provided this as our facility's standing nursing protocol consistent with the admission agreement.

## **If my resident refused the last iodophor dose, am I supposed to offer it again?**

This protective regimen should be encouraged among residents. If a resident refused their medication, staff would try to encourage the resident to take it at a later time. Similarly, if a resident refused a bath, staff would try to encourage a bath at a later time. Staff need to assess whether the resident is refusing at this time (e.g. tired, in pain, irritable), or whether the resident is refusing all further doses and if the resident understands the reason and the value of the iodophor (e.g. to prevent infection due to MRSA and other bacteria).

## **My resident left our nursing home, but has been readmitted. Do they need to receive iodophor again?**

Yes. Regardless of prior receipt, iodophor should be administered each time a resident is admitted to your nursing home to ensure residents are protected for their entire stay.

## **What if the resident develops a reaction?**

Similar to all quality improvement interventions, if a problem arises, it should be brought to the attention of the treating nurse and physician, who will decide all necessary actions related to discontinuing product and ordering any medications to address the reaction.

## Decolonization Do's and Don'ts

### DO

- Begin decolonization on admission to remove germs as soon as possible
- Use chlorhexidine (CHG) for all bathing/showering needs for all residents
- Use 2% no-rinse CHG cloths for bed baths *or* 4% rinse-off liquid CHG for showers
- Use CHG for regular bathing during resident's entire nursing home stay
- Massage CHG onto skin for best effect
- Use CHG on lines, tubes, drains, and over non-gauze dressings
- Use on superficial wounds and rashes to remove germs
- Use nasal iodophor treatment twice a day for a 5-day period every other week
- Report iodophor/CHG related events to treating physician and nursing director

### DON'T

- Do NOT get CHG into eyes or ears
- Do NOT wipe off after applying CHG cloths. Let air dry.
- Do NOT flush CHG cloths. Place in trash.
- Do NOT continue protocol after discharge
- Do NOT use protocol on residents <18 years old
- Do NOT use iodophor and/or CHG on resident if resident is allergic

**REFER TO NURSING PROTOCOL FOR STEP-BY-STEP INSTRUCTIONS**

---

PROTECTING NURSING HOME RESIDENTS FROM INFECTIONS AND READMISSIONS

---

## Resident Talking Points

### This section includes:

- Resident Talking Points on Chlorhexidine Bathing
- Resident Talking Points on Nasal Iodophor

---

**PROTECTING NURSING HOME RESIDENTS FROM INFECTIONS AND READMISSIONS**

---

### **Resident Talking Points Chlorhexidine Bathing**

Residents may have questions regarding CHG bathing and nasal iodophor. Below are some suggested responses to common resident questions.

**REMEMBER:** Your **enthusiasm** and **encouragement** will be the greatest predictor of a resident's acceptance and support for this infection prevention protocol.

#### **What are these cloths for?**

"This is your protective bath while you are staying at this nursing home. All residents here are provided this bath to prevent infection. This type of bathing uses a special soap called chlorhexidine which is deeply cleansing and works better than regular soap and water to remove germs and protect you from infection. It has been used on millions of patients in many hospitals and some nursing homes across the country to clean the skin and protect from germs."

#### **How do you know it works better than soap?**

"We are using the chlorhexidine soap because it has been proven to get rid of body germs and prevent infections in large clinical trials in U.S. hospitals. In those studies, antibiotic-resistant bacteria dropped by almost 40% and bloodstream infections dropped by 50%."

#### **I don't feel as clean after bathing with the cloths.**

"I know we usually think of baths as having soapy water, but while you still require medical care at this nursing home, these cloth baths work better than soap and water to remove germs from the skin. It is deeply cleansing and will protect you more than soap and water."

### **Why do these cloths leave my skin feeling sticky?**

“I should have mentioned the brief sticky feeling before you started to use them. It’s actually a good thing. The sticky feeling is due to the aloe vera in the cloths which moisturizes your skin while it cleans. The aloe is the sticky feeling that goes away after a few minutes and leaves your skin soft and moisturized.”

### **Can I use my own soap and/or lotions along with this bath?**

“No, other soaps and lotions may prevent this bath from working and may not protect you because they interfere with the germ-fighting ingredient in the soap. This bath works better than soap and water to protect you, so it is important that you only use the soap we give you during your stay.”

### **I would prefer to use my own shampoo and face soap. Is this okay?**

“Other soaps and shampoos may interfere with the CHG soap which works the best to remove germs from your body. We strongly encourage you to use the CHG while you are here. However, if you must use your own shampoo or face soap, please use them first and try to keep the shampoo and face wash off of the body so CHG will work as body soap.”

### **I am too tired and I don't feel like bathing.**

“I understand you must be tired, but this bath is important to protect you from bacteria and germs. It will only take 5 to 10 minutes and will make you feel refreshed. I will help you. If you are too tired right now, I can come back later and check in with you.”

### **I don't think I can bathe because I have an IV.**

“Don't worry, we do this all the time. In fact, because you have lines, it's even more important to keep germs off the skin and prevent infection. We actually clean the lines after we clean your skin. I will help you with areas around the lines and any other hard to reach areas.”

### **Can I wait to bathe tomorrow? I just arrived today.**

“Your first day in a nursing home is the most important day to take a bath and protect you from germs before we begin your medical care here. Bathing takes only 5-10 minutes and will make you feel refreshed and clean.”

### **I would prefer to perform my own bed bath.**

“If you wish to bathe yourself, let me give you important instructions and a handout (“CHG Bathing for Residents”). Remember to read the instructions carefully, as the bath may not protect you if it is not done correctly. The CHG cloths have a special no-rinse soap that works better than soap and water to

remove germs that can cause infection. Massage the skin well with the cloths to remove skin germs. Don't rinse since the CHG continues to work for 24 hours to keep germs away. Don't forget to clean all skin areas, including the neck and skin folds. Most residents need some help. I can help you with any hard to reach areas as well as help you clean on and around your lines or drains."

### **Can I use the soap on wounds or skin rashes?**

"Yes. In fact, cleaning skin wounds and rashes is particularly important since germs can get under the skin when there is a skin break. You should also use the cloth over plastic dressings and to clean 6 inches of any line, tube, or drain closest to your body. I will help you with that part of your bath."

### **The label for liquid CHG says it can be used for routine bathing (skin, wound, and general skin cleansing), but CHG cloths are labeled as preoperative. Is it okay to use the cloths for routine bathing?**

"Yes, both CHG liquid and CHG cloths are safe to use for routine bathing. The cloths are labeled based upon the original studies performed by the manufacturer to market the product. Since then, many large clinical trials have now shown that routine CHG bathing reduces serious infections, even in critically ill residents. The manufacturer came to this nursing home to help train the staff on use of this product for routine bathing based upon these trials. In fact, 80% of US hospitals now use CHG as their soap for routine bathing of ICU patients. This type of routine bath has been used in hundreds of thousands of patients and is well-tolerated and safe. Our goal is to prevent infection and protect you while you are here."

**PROTECTING NURSING HOME RESIDENTS FROM INFECTIONS AND READMISSIONS**

## **Resident Talking Points**

### **Nasal Iodophor**

Residents may have questions regarding nasal iodophor. Below are some suggested responses to common resident questions.

#### **REMEMBER:**

- Your **enthusiasm** and **encouragement** will be the greatest predictor of a resident's acceptance and support for the protocol.
- Exclude residents with known allergy to iodine.

#### **A. How to introduce iodophor swabs to residents:**

"Good morning Ms/Mr X, every other week, our nursing home provides all residents with iodophor swabs to remove bacteria from the front of the nose. Some bacteria that you may have heard of, like "MRSA," live in the front of the nose and can cause future infections. Studies have found that one-third to one-half of nursing home residents have MRSA so we want to protect all our residents from infection by giving this swab to get rid of those germs. Would that be okay?"

Have you had this swab in your nose before? It's called iodophor, also known as povidone iodine. We use one swab in each nostril for about 30 seconds, or at least 3 times around slowly.

Our doctors are offering this to all residents Monday-Friday every other week. We give it twice a day. The goal is to protect all residents at the same time."

